14/6/2025

NCT: 05893823

Retrospective study on radiological factors predictive of symptomatic psoas impingement development in protruding cups in primary hip arthroplasty

INTRODUCTION

Groin pain after total hip arthroplasty (THA) is a relatively rare condition, with reported incidence ranging from 0.4% to 18.3%. The most common intrinsic causes of groin pain include infection, aseptic loosening, impingement, and fractures. Iliopsoas (IP) tendinopathy following THA is an insidious and often underdiagnosed condition, affecting between 0.37% and 4.3% of implanted hips.

IP tendinopathy arises from friction, irritation, and mechanical stress on the tendon, often due to impingement. Both direct and indirect causes have been identified. In press-fit acetabular components, direct causes include prominent or malpositioned cups, lack of anterior bony coverage, and screw protrusion. Indirect causes, such as increased offset and leg length discrepancy, have been inconsistently reported in the literature.

Acetabular cup protrusion on axial imaging has been identified as the most sensitive and specific predictor of symptomatic IP impingement. However, cup prominence is also frequently seen in asymptomatic THAs. According to the literature, other radiological parameters—beyond cup prominence—may influence or predict the onset of IP impingement. Thus, cup protrusion alone seems to be a necessary but not sufficient condition for the development of IP tendinopathy.

The aim of this study is to compare a retrospective cohort of patients with acetabular cup protrusion who did not develop symptoms compatible with IP tendinopathy, with a group of patients who did present with symptomatic cup prominence and were treated with arthroscopic IP tenotomy. Post-THA CT scans were analyzed to identify which radiological or positional factors (e.g., inclination, version, offset, leg length discrepancy, and reaming technique) could predict the onset of IP impingement in patients with prominent acetabular cups.

OBJECTIVES, STUDY DESIGN, AND POPULATION

The objective of this study is to identify post-operative CT-based radiological predictors of symptomatic IP tendinopathy in patients with acetabular cup prominence. The analysis compares asymptomatic and symptomatic patients, the latter having undergone arthroscopic tenotomy for IP tendinopathy. All patients were treated at the IRCCS Istituto Ortopedico Rizzoli, Department of Orthopaedics, Trauma and Hip/Knee Arthroplasty and Revision Surgery, between 2000 and 2021.

This is a retrospective observational cohort study. The study population includes adult patients who underwent primary THA and subsequently had a post-operative CT scan performed for pain, clicking, or contralateral hip planning.

Inclusion criteria: primary THA, post-op CT scan available for pain, clicking or contralateral planning; minimum 5-year follow-up for the control group and history of IP tenotomy for the symptomatic group; complete clinical and radiological documentation.

Exclusion criteria: patient refusal; inadequate CT or CT performed for periprosthetic fracture, loosening, infection, or obvious wear; incomplete documentation; insufficient follow-up or resolved symptoms after conservative treatment.

ENDPOINTS AND OUTCOME MEASURES

The primary endpoint is the identification of CT-based radiological predictors of IP tendinopathy in patients with acetabular cup prominence after THA. These include acetabular version, inclination, offset, and reaming technique.

MATERIALS AND METHODS

This study evaluates the radiological predictors of symptomatic IP tendinopathy in a cohort of adults who underwent primary THA and exhibited acetabular cup prominence on post-operative CT. All patients were treated at the IRCCS Istituto Ortopedico Rizzoli between 2000 and 2021. Post-operative CT scans were reviewed, and cases with prominent acetabular cups were selected. Demographic, surgical, and follow-up data were retrieved from the medical records and routine clinical documentation.

Patients were stratified based on the presence or absence of IP tendinopathy. Symptomatic patients had to have undergone IP tenotomy after thorough diagnostic evaluation, including clinical tests, US-guided anesthetic injection (with failed response to multiple infiltrations), serial X-ray, CT, and lab testing to rule out other causes. This diagnostic workflow is supported by the international literature.

The control group included patients with cup prominence who remained asymptomatic during at least 5 years of follow-up.

COLLECTED VARIABLES

Demographic variables: sex, age at primary THA, operated side, underlying diagnosis.

Implant-related variables: cup type and size, stem type, head diameter, bearing couple, time between THA and CT.

Cup prominence variables: axial and sagittal prominence in mm.

CT-based outcome measures:

- Acetabular version (°)
- Contralateral acetabular version (°)
- Version difference (°)
- Cup inclination (°)
- Femoral offset (mm)
- Acetabular offset (mm)

- Global offset (cm)
- Contralateral global offset (cm)
- Offset difference (cm)
- Acetabular diameter (mm)
- Diameter mismatch (mm)
- Eccentric reaming (mm)

Measurements will be validated through intra- and inter-observer reliability testing. Outcomes will be analyzed to identify radiological predictors of IP tendinopathy. The ultimate goal is to define intraoperative positioning strategies to reduce the risk of developing symptoms.

DATA ANALYSIS

Quantitative variables will be expressed as mean, standard deviation, minimum, and maximum values. Qualitative variables will be reported as frequencies and percentages. Inter- and intra-observer reliability will be assessed using correlation statistics with 95% confidence intervals and standard error. Differences between symptomatic and asymptomatic patients will be evaluated using the Mann-Whitney U test for continuous and discrete variables, and Chi-square test for categorical variables. All analyses will be performed using IBM SPSS version 25 or later. Statistical significance is set at $p < 0.05$.

STUDY TIMELINE

Start date: Date of Ethical Committee (EC) approval.

- Step 1: Kickoff meeting within 2 months of EC approval to plan the project phases, data collection, storage, analysis, and publication.
- Step 2: Data collection from month 2 to 12 post-kickoff.
- Step 3: Data analysis with involvement of all investigators.
- Step 4: Data publication.

End date: Within 18 months from EC approval (12 months for data collection, 6 months for analysis and publication).

DATA COLLECTION AND STORAGE

Clinical data will be extracted from patient medical records and source documents. A standardized Case Report Form (CRF) will be used to collect relevant clinical and radiographic data. All data will be pseudo-anonymized using a unique patient code. The database will be stored in a password-protected computer accessible only to the investigators.

ETHICAL CONSIDERATIONS

The study protocol and all relevant documents will be submitted for approval to the competent authorities and Ethics Committee prior to study initiation. The study will comply with the principles of the most recent Declaration of Helsinki (Fortaleza, October 2013), as well as all applicable national and international regulations concerning clinical research. The protocol was written and the study will be conducted in accordance with ICH-GCP guidelines.

INFORMED CONSENT

As IRCCS Istituto Ortopedico Rizzoli is a recognized research institute, patient data used for research purposes are governed by Article 110-bis, paragraph 4 of the Italian Privacy Code (D.lgs 196/2003 as amended by D.lgs 101/2018). Therefore, specific consent for data processing is not required.

PRIVACY

All patients will be identified by a numerical code to ensure pseudo-anonymization. Data will be processed in compliance with current national and European privacy laws. Access to sensitive data will be restricted to study sponsors and designated personnel for monitoring/auditing purposes, the principal investigator and collaborators, the Ethics Committee, and relevant health authorities. Access to source documentation for audits or inspections will be granted while maintaining patient confidentiality.

FINAL REPORT AND PUBLICATION

The principal investigator commits to producing a final report and publishing the study results, regardless of outcomes, as described in the protocol. Any publication or dissemination (journals, conferences, seminars) will occur only after statistical processing and always in fully anonymous form.

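### Screw protrusion, which the protocol names as a direct cause of iliopsoas tendinopathy, is neither recorded nor an explicit exclusion, so it may act unseen among the symptomatic hips.

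*Combined protocol and SAP*

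**What the plan says.** The Introduction lists the direct causes of iliopsoas tendinopathy with press-fit cups: "direct causes include prominent or malpositioned cups, lack of anterior bony coverage, and screw protrusion". It then argues that a protruding cup is required for the condition but does not explain it alone. The aim is to find which radiological or positional factors predict symptoms among prominent cups. The factors in brackets there are given as examples, not as a closed list.

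Under Materials and Methods, prominence is the entry condition: "Post-operative CT scans were reviewed, and cases with prominent acetabular cups were selected". Controls meet it too: "The control group included patients with cup prominence who remained asymptomatic during at least 5 years of follow-up". Symptomatic patients must have had a tenotomy after a work-up that includes "serial X-ray, CT, and lab testing to rule out other causes".

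The exclusion criteria that concern the CT are "inadequate CT or CT performed for periprosthetic fracture, loosening, infection, or obvious wear". Under Collected Variables, the implant items are "cup type and size, stem type, head diameter, bearing couple, time between THA and CT", followed by "Cup prominence variables: axial and sagittal prominence in mm" and 12 CT measures of version, inclination, offset, diameter and reaming. No item in these lists concerns screws.

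Data Analysis says that group differences are "evaluated using the Mann-Whitney U test for continuous and discrete variables, and Chi-square test for categorical variables". It describes no adjusted or stratified analysis.

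**The concern.** Both groups have a prominent cup by design, so the study is a search for what else distinguishes symptomatic hips. A protruding screw is a candidate on the protocol's own account, and it is a radiological feature that falls within an objective of finding CT-based predictors. If it is not recorded, three things follow.

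- It cannot emerge as a predictor, even if it is one.
- If some symptomatic hips are symptomatic because of a screw and their cup position is like that of controls, they pull the group difference in version, inclination or offset toward zero.
- If screw use goes with cup type or cup position, part of an observed position difference could belong to the screw.

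The stated end use is guidance on how to place the cup at surgery, so a missed or misattributed difference would carry into that guidance.

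**Working it through.** **Step 1. Trace screw protrusion through the plan.**

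| Place in the protocol | Is screw protrusion handled? |
|---|---|
| Introduction, direct causes | Named |
| Exclusion criteria | Not mentioned |
| Symptomatic work-up (Materials and Methods) | Other causes are to be ruled out, but none are listed |
| Implant-related variables | Not listed |
| Cup prominence variables and the 12 CT measures | Not listed |
| Data Analysis | Unadjusted tests only |

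The work-up does not clearly close the gap. Its purpose is to establish iliopsoas tendinopathy as the source of pain. By the Introduction, a protruding screw is itself a cause of iliopsoas tendinopathy, so a tendon irritated by a screw could satisfy the work-up.

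**Step 2. Trace anterior bony coverage the same way.** It is not a named variable. Axial and sagittal prominence, version, diameter mismatch and eccentric reaming are all collected, however, and bear on how far the cup is uncovered. Coverage is therefore captured indirectly.

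**Step 3. Size of possible dilution.** The plan states no sample size, power, effect or screw frequency, so there is no figure to reproduce. All inputs here are assumptions:

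- true difference for position-related cases: 0.7 SD
- 25 symptomatic and 50 asymptomatic patients
- two-sided alpha 0.05 (the plan gives 0.05 without stating the sidedness)
- efficiency of the Mann-Whitney test relative to the t-test: 0.955
- a share f of cases is screw-caused, with cup position like that of controls

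Observed difference = 0.7 × (1 − f).

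Power ≈ Φ( 0.7 × (1 − f) × √(0.955 × 25 × 50 / 75) − 1.96 ), where √(0.955 × 25 × 50 / 75) = √15.917 = 3.990.

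The sample size needed to restore power grows by 1 / (1 − f)².

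| f | Difference (SD) | Difference × 3.990 | Power | Sample size factor |
|---|---|---|---|---|
| 0 | 0.700 | 2.793 | 0.80 | 1.00 |
| 5% | 0.665 | 2.653 | 0.76 | 1.11 |
| 10% | 0.630 | 2.513 | 0.71 | 1.23 |
| 20% | 0.560 | 2.234 | 0.61 | 1.56 |
| 30% | 0.490 | 1.955 | 0.50 | 2.04 |

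The result does not hinge on 0.7 SD or on 25 versus 50. A 0.5 SD difference with 63 per group (normal approximation for two means) also starts at 0.80 and falls to 0.76, 0.71, 0.61 and 0.50. With power starting at 80%, the loss depends on f alone. Whether the study starts near 80% is not known.

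**Step 4. Confounding.** Dilution of this kind moves results toward no difference and does not create a false predictor. A spurious cup-position finding would need screw protrusion to be associated with the position variables. The documents are silent on that, so no figure is offered.

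**The case against.** The strongest reply is that the case definition already protects the comparison. The Introduction describes the symptomatic group as patients whose cup prominence was symptomatic, and the work-up includes CT. A hip judged painful because of a screw might not have been classed that way. This has some force: the documents do not show that any screw-caused case was enrolled. A reader might infer that such cases are in the group and are being attributed to cup position; the text supports only that some may be. The reply does not remove the gap, because neither statement mentions screws and nothing recorded would allow a check.

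A reader might also infer that anterior coverage goes unmeasured. That is too strong, given the indirect measures in step 2. Nor do the documents treat poor coverage as a cause clearly separate from a prominent cup.

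A third tempting inference is that the study passes over direct causes in favour of lesser ones. The Introduction does not support this. Malpositioned cups are on the same list of direct causes, and version and inclination address them; only offset and leg length are called indirect.

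Finally, the power figures rest on no document input, and they take screw-caused cases to have fully control-like position. Every such hip also has a prominent cup, so a screw may be an additional cause and the loss smaller. That objection stands, and the figures are an illustration only.

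**Conclusion.** The point holds for screw protrusion. The protocol names it as a direct cause, neither records it nor explicitly excludes it, and plans tests that could not detect or correct for it. Some symptomatic hips may have a screw as a competing or additional cause, with dilution or, under a further condition, confounding of the cup-position differences.

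The size cannot be determined from the documents. Under the stated assumptions, power of 0.80 becomes 0.76 if 5% of cases are screw-caused and 0.50 if 30% are; with none, nothing is lost. For anterior bony coverage, the supported statement is only that it is captured indirectly and that its relation to the prominence measures is not spelled out. This is an inexpensive improvement to a study seeking CT predictors, and does not show that its results would be wrong.

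**What to change.** On the existing CT scans, in both groups and by the same readers, record:

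- screws present (yes/no)
- screw protrusion toward the iliopsoas (yes/no, and mm)

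Add these to Collected Variables and compare them between groups as candidate predictors, using the tests already planned. Prespecify in Data Analysis a sensitivity analysis that repeats the main comparisons without hips showing screw protrusion. If no screw protrudes in either group, one sentence in the report settles the matter. A line saying which collected measures stand for anterior coverage would also help and needs no new reading.

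No new imaging, patients or staff are needed. The cost is somewhat more reading time, inclusion of the new readings in the intra- and inter-observer reliability testing that the protocol requires of its measurements, and one or two more candidate variables in the multiplicity count. The sensitivity analysis will have fewer hips and should be read as a check on the direction and size of the differences, not on whether p stays below 0.05.

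### A group difference in version difference or offset difference could reflect the reference hip instead of cup placement, because neither CT indication nor contralateral hip status is a listed variable

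*Combined protocol and SAP*

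**What the plan says.** - **Entry (Objectives, Study Design, and Population).** Eligible patients had primary THA and "subsequently had a post-operative CT scan performed for pain, clicking, or contralateral hip planning". The same three indications apply to both groups. Symptoms that resolved with conservative treatment are an exclusion.
- **Controls (end of Materials and Methods).** "The control group included patients with cup prominence who remained asymptomatic during at least 5 years of follow-up". Two other wordings are looser. The Introduction describes controls as patients "who did not develop symptoms compatible with IP tendinopathy", and Materials and Methods says "Patients were stratified based on the presence or absence of IP tendinopathy".
- **Cases (Materials and Methods).** They had iliopsoas tenotomy after a work-up of the replaced hip that included CT. No criterion concerns the other hip.
- **Measures (Collected Variables).** Version is listed for the operated side, the contralateral side and as a difference. Global offset is listed in the same three ways. No formula is given for either difference. Neither the reason for the CT nor the state of the contralateral hip appears in the list.
- **Analysis (Data Analysis).** Two-group Mann-Whitney and Chi-square tests at p < 0.05, without adjustment.
- **Endpoint and use.** Of the predictors, the primary endpoint says: "These include acetabular version, inclination, offset, and reaming technique". Collected Variables adds: "The ultimate goal is to define intraoperative positioning strategies to reduce the risk of developing symptoms".

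**The concern.** A side-to-side difference is informative about cup placement only if the reference hip is comparable between the groups, and selection may break that here. A patient who stays free of symptoms has little reason for a CT because of pain or clicking in the replaced hip, so planning for the other hip is the natural route into the control group. In those patients the other hip is, by the nature of the scan, a candidate for surgery. Cases enter because of the replaced hip and are not selected on the other one.

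If diseased or replaced reference hips measure differently, the two differences can separate the groups even when cups were placed identically. The stake is interpretation. The Introduction lists increased offset among the suspected indirect causes, and offset difference is the listed measure closest to that idea. A significant result could be turned into positioning advice when only the reference hip differs.

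**Working it through.** The documents give no sample size, SD, effect size or split by CT indication, so there is no figure of the plan's own to reproduce. The mechanism follows from the text; the numbers below are illustrative only.

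**Mechanism.** Let O be the operated-side value, C the contralateral value and D = O − C. Suppose O has the same distribution in both groups, and affected (diseased or replaced) reference hips have C shifted by s. If the affected share is p₁ in controls and p₀ in cases, then

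mean D (cases) − mean D (controls) = s × (p₁ − p₀).

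This is zero if the shares are equal, or if s has no consistent sign and averages out. Tests on O alone do not involve C.

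**Assumed inputs (none from the documents).** 30 cases and 60 controls; SD of D 7 mm for offset; equal SDs on the two sides with correlation 0.5; s = 2 or 3 mm; normal data; two-sided Mann-Whitney at 0.05; 20,000 simulated datasets per cell; no true placement effect.

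| Affected, controls vs cases | s = 2 mm: spurious difference | false positives | s = 3 mm: spurious difference | false positives |
|---|---|---|---|---|
| Equal shares | 0 | 5.0% | 0 | 5.0% |
| 80% vs 50% | 2 × 0.3 = 0.6 mm | 6.4% | 3 × 0.3 = 0.9 mm | 8.5% |
| 70% vs 30% | 2 × 0.4 = 0.8 mm | 7.6% | 3 × 0.4 = 1.2 mm | 10.9% |
| 100% vs 30% | 2 × 0.7 = 1.4 mm | 14.2% | 3 × 0.7 = 2.1 mm | 24.9% |

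**Hand check of one cell.** The standard error of the difference in means is 7 × √(1/30 + 1/60) = 1.57 mm. For 70% vs 30% and 3 mm, 1.2/1.57 = 0.77 standard errors. The normal approximation gives P(Z > 1.96 − 0.77) + P(Z < −1.96 − 0.77) ≈ 12%, close to the simulated 10.9%.

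**Range.**
- A shift of random sign gives 4–5% in the three unequal contrasts.
- A 5 mm shift gives 14.6%, 22.0% and 55.7% for the three unequal rows in table order.
- Version difference with assumed SD 8° and shifts of 2° or 3° gives 6.0% or 7.6% (80% vs 50%), 6.7% or 9.6% (70% vs 30%), and 11.6% or 20.2% (100% vs 30%).

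**How far the contralateral row helps.** The same shift appears directly in C. Since SD(D) = SD(C) × √(2(1 − r)), SD(C) is 7 mm at r = 0.5 and 9.9 mm at r = 0.75, so a 1 mm shift is no easier to see there than in D. With moderate imbalance, when D is falsely significant, C is also significant in 24–31% of datasets (r = 0.5) or 14–17% (r = 0.75). Some of those significant D results are ordinary chance errors that no reference-hip check could be expected to flag, so these percentages understate the value of the row. Read as estimates with confidence intervals, it is more useful than its p-value suggests.

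**The case against.** The strongest reply is that the problem needs several conditions, none of which the documents show: controls mostly from planning CTs, abnormal contralateral hips clearly less common in cases, a shift in one direction, and differences that are in fact side-to-side. If the second or third fails, the false-positive effect disappears. This stands, and it is why the point is worded as a possibility. The looser control wordings could also admit patients scanned for pain of another origin. But the listed variables give no way to check the split, which is the reason to tabulate it.

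It can also be said that contralateral version and contralateral global offset are already listed and tested. That is a real safeguard, but a partial one. Without hip status, a shift in that row cannot be explained or removed, and the plan does not say how to read the rows together. Eligibility cannot be applied without knowing the CT indication, and the CRF described under Data Collection and Storage may hold both fields. If so, listing them costs almost nothing.

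Three stronger readings are tempting and are not supported:

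- **That controls do come from planning CTs and the results are biased in a known direction.** The documents give neither the split nor the direction.
- **That the primary endpoint is undermined.** It names no difference measure, and operated-side version, inclination, operated-side offset and cup prominence do not use the other hip.
- **That an opposing shift would hide a real effect from the study.** For an assumed 4.9 mm operated-side effect (0.7 SD of D) and an opposing 3 mm shift at 70% vs 30%, power for D falls from 85% to 60%. The operated-side test is untouched by the shift, at 85% (r = 0.5) or 57% (r = 0.75). The chance that at least one of the two is significant falls only from 94% to 90%, or from 90% to 78%.

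**Conclusion.** The concern holds in a limited form. As planned, a group difference in version difference or offset difference cannot be attributed to cup placement with confidence, because the reference hip may differ between the groups through selection and the listed variables do not allow this to be examined. It affects these two measures only.

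With moderate imbalance and a consistent 2–3 mm shift, the error rate is modestly above nominal. Rates of 14–25% require the extreme 100% vs 30% contrast. All of these rest on assumed inputs. The confidence is medium: the gap in the variable list and the unadjusted tests are plain in the text, but the imbalance and the consistent shift are not. The change is worth making because it is cheap and the ambiguity bears on the study's stated goal.

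**What to change.** 1. Under Collected Variables, add CT indication and contralateral hip status at CT (native without disease, diseased, or prosthetic). Tabulate both by group.
2. Define version difference and offset difference. Report each beside its operated and contralateral components, with group differences and 95% CIs. Rest positioning conclusions on the operated-side measures.
3. Keep the full-sample comparison. Add a sensitivity analysis of the two differences that excludes prosthetic contralateral hips and compares groups within the same contralateral status. Pool over statuses where both groups are represented, and keep it descriptive with CIs where strata are small.
4. Do not adjust for CT indication, which may nearly coincide with group.

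**Cost.** Two fields read from records and scans already in use, some analysis wording, and a less precise sensitivity analysis. On the assumptions above, a linear model with group and status holds false positives at about 5%. Its 95% CI half-width is 3.26 mm (80% vs 50%) or 3.35 mm (70% vs 30%), against 3.11 mm unadjusted. Power for 4.9 mm is 81–84%, against 87% for the unadjusted t-test. If only the diseased stratum is usable, precision drops. With 15 cases and 48 controls (30 × 0.5 and 60 × 0.8) the half-width is 4.14 mm; with 9 and 60 (30 × 0.3 and 60 × 1.0) it is 4.99 mm. Excluding prosthetic contralateral hips could widen these further.

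### Entry rules tied to different time spans, an undefined 2000-2021 window and no listed THA year leave surgical era unchecked in an unadjusted comparison

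*Combined protocol and SAP*

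**What the plan says.** The inclusion criteria (Objectives, Study Design, and Population) ask for "minimum 5-year follow-up for the control group and history of IP tenotomy for the symptomatic group". Materials and Methods repeats the control rule: "The control group included patients with cup prominence who remained asymptomatic during at least 5 years of follow-up". The exclusion criteria remove "insufficient follow-up or resolved symptoms after conservative treatment", with no threshold and no statement of which group this applies to.

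The calendar frame is given as "All patients were treated at the IRCCS Istituto Ortopedico Rizzoli between 2000 and 2021". The event that must fall in those years is not named, and no closing date for follow-up is given. The Study Timeline is counted from ethics approval, without a calendar date.

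Collected Variables has two relevant lines: "Demographic variables: sex, age at primary THA, operated side, underlying diagnosis" and "Implant-related variables: cup type and size, stem type, head diameter, bearing couple, time between THA and CT". Time from THA to CT is the only interval listed. THA date or year, follow-up duration, and time from THA to symptoms or tenotomy are absent. Materials and Methods adds, in general terms, "Demographic, surgical, and follow-up data were retrieved from the medical records and routine clinical documentation".

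Data Analysis compares the groups by "Mann-Whitney U test for continuous and discrete variables, and Chi-square test for categorical variables". It mentions no matching, stratification or regression.

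**The concern.** A hip implanted late in the window can become a case as soon as tenotomy is done, but can become a control only after five further years without symptoms. Depending on what the window bounds and when follow-up closes, the most recent years may supply cases and no controls. The case and control series may also be spread differently over the 22 years for other reasons.

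The candidate predictors (version, inclination, offset, reaming technique) are fixed at surgery and could plausibly drift with implant design and surgical habit over such a period. If they drift and the groups come from different years, an unadjusted test can show a difference that has nothing to do with symptoms. This matters because the protocol intends the findings to inform how cups are positioned during surgery.

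**Working it through.** The plan states no sample size, effect size or event count, so it has no figure to reproduce. The check has two parts.

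**1. How far the entry rules alone can separate the groups**

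Inputs from the documents: window 2000-2021 (22 years), five-year minimum for controls, document date 14/6/2025. Assumptions: the window bounds THA; THA dates are uniform over each group's eligible years; cases can be implanted up to the end of 2021.

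Latest control THA = follow-up cut-off minus 5 years. Case-only share = (2022 - latest control THA) / 22. Gap in mean THA date = (2000 + 2022)/2 - (2000 + latest control THA)/2.

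| Follow-up closes | Latest control THA | Case-only share | Mean gap |
|---|---|---|---|
| End of 2021 | 2017.0 | 5/22 = 23% | 2011.0 - 2008.5 = 2.5 years |
| 14/6/2025 | 2020.45 | 1.55/22 = 7% | 2011.0 - 2010.2 = 0.8 years |
| End of 2026 | 2022.0 | 0% | 0 |

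In days, the second row is 14/6/2020 to 31/12/2021 = 565, and 565/8036 = 7.0%. The first row is closer to an upper figure: if tenotomy must also fall by the end of 2021, late-implanted cases would be thinned too and the gap would shrink.

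**2. What such a gap does to one test**

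Take a measurement unrelated to symptoms that drifts linearly with THA year. The spurious group difference in SD units is drift per decade x gap / 10. At a drift of 0.5 SD per decade:

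- 0.8-year gap: 0.5 x 0.775/10 = 0.04 SD
- 2.5-year gap: 0.5 x 2.5/10 = 0.125 SD
- 7.5-year gap: 0.5 x 7.5/10 = 0.375 SD

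The 7.5-year gap is an assumed clustering: cases implanted 2010-2021 (mean 2016.0) and controls 2000-2016 (mean 2008.5).

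False-positive rates come from simulating a two-sided Mann-Whitney test at 0.05, with 4,000 runs per cell. The Monte Carlo standard error near 5% is sqrt(0.05 x 0.95/4000) = 0.3 percentage points. Drift and group size are assumptions.

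| Gap | Drift (SD/decade) | n = 25 per group | n = 50 | n = 100 |
|---|---|---|---|---|
| 0.8 years | 0.5 | 5.9% | 5.1% | 5.4% |
| 0.8 years | 1.0 | 5.2% | 6.8% | 7.0% |
| 2.5 years | 0.25 | 4.8% | 5.8% | 7.3% |
| 2.5 years | 0.5 | 6.4% | 9.2% | 13.2% |
| 2.5 years | 1.0 | 10.8% | 19.0% | 31.5% |
| 7.5 years | 0.25 | 8.8% | 14.8% | 25.6% |
| 7.5 years | 0.5 | 23.7% | 43.0% | 71.3% |

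With no drift the rate is about 5% (4.4% to 5.2%). Truncation at the document date barely moves the error rate. Truncation at the end of 2021 matters only with strong drift or larger groups. The large figures need the assumed clustering.

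**The case against.** The unequal entry rules are not in themselves an error. Cases are defined by an event and controls by its absence, so a symptom-free minimum for controls is a sensible guard against counting future cases as controls. This stands.

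A reader might infer that cases need no follow-up at all. The text does not go that far. The exclusion for insufficient follow-up is not confined to controls, and cases must have completed a long work-up with repeated failed injections. The case requirement is unstated, which is different from absent.

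A reader might also infer that an era imbalance could be neither detected nor corrected. That is too strong. Age at THA, time from THA to CT and the five-year check all need the THA date, surgical data are said to be retrieved, and the CRF itself is not shown. Cup type, head diameter and bearing couple may partly reflect era. What remains is that the variable list does not include THA year and that no planned analysis uses it or these proxies.

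A third tempting inference is that unequal time at risk itself produces false predictors. Cup position is fixed at surgery, so time at risk acts mainly through controls who become symptomatic after year 5. That usually dilutes a true difference. Five years is also a minimum for controls and not a cap.

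Finally, the entry rules alone cannot be shown to cause a large shift. Suppose a measurement changed by 5 degrees between the two halves of the window (an assumption). With uniform dates and a 14/6/2020 control cut-off, 50% of cases and 9.45/20.45 = 46.2% of controls fall in the later half, a spurious difference of 5 x 0.038 = 0.19 degrees. With controls ending in 2016, the control share is 6/17 = 35.3% and the difference 5 x 0.147 = 0.74 degrees. Anything much larger needs a clustering of dates that the documents do not report.

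**Conclusion.** The point holds as a gap in definition, recording and analysis. The window has no stated bounding event, follow-up has no closing date, THA year and time to symptoms or tenotomy are not listed, and the comparison is unadjusted. A period effect could therefore be reported as a positional predictor without the planned analysis revealing it.

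The size cannot be determined from the documents. The case-only share of the window is 23%, 7% or 0% according to when follow-up closes, given uniform THA dates and a window that bounds THA. Under the last two readings, truncation alone is minor. Serious inflation requires either strong drift with the 2.5-year gap or cases and controls concentrated in different years. The documents show neither, and they do not rule either out. The point is worth fixing because the check is cheap and the results are meant to guide surgery; it does not show that the planned comparison is biased.

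**What to change.** Keep the five-year symptom-free minimum for controls. Then:

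- State which event 2000-2021 bounds (THA, CT or tenotomy), and give the follow-up cut-off date.
- Add THA year, follow-up duration, and time from THA to symptom onset or tenotomy to the CRF.
- Report THA year by group alongside the baseline variables.
- Add one sensitivity analysis of the primary comparison, limited to THA years in which both groups were eligible and stratified by THA period, for example a van Elteren test or a regression that includes THA year.

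A further restriction to cases with onset within five years of THA is optional and secondary, because it would remove an unknown number of cases.

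The cost is two or three fields from existing records, one additional analysis, and a few late-window cases left out of that sensitivity analysis only.
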